#### **Adverse Events**

The terms used in the eCRFs by investigators to identify adverse events will be coded using the Medical Dictionary for Regulatory Activities (MedDRA). All reported adverse events with onset during the treatment phase (ie, treatment-emergent adverse events) will be included in the analysis. Additionally, a summary of all reported adverse events (regardless of whether treatment-emergent) will also be provided.

For each adverse event, the percentage of subjects who experienced at least 1 occurrence of the given event will be summarized by treatment group. The percentage of subjects with specific treatment-emergent adverse events will be summarized by severity and relationship to study drug, as classified by the investigator, by treatment group.

Special attention will be given to those subjects who died, or who discontinued treatment due to an adverse event, or who experienced a severe or a serious adverse event (eg, summaries, listings, and narrative preparation may be provided, as appropriate).

Further analyses, to be described in the SAP for this study, will be conducted on the pre-specified adverse events for which additional information is collected from the investigators (refer to Section 9.8, Safety Evaluations), and on other adverse events.

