# 10.2.4. Comprehensive Follow-up at Scheduled Study Visits Following Premature Discontinuation of Study Drug

It is important to note that subjects who discontinue study drug early will be required, wherever possible, to continue with scheduled visits for the duration of the study. Data collection required for subjects who discontinue study drug early will be comprehensive (as described in the Time and Events Schedule) and will be essential for every randomized subject. Subjects will continue to be followed up for specific data collection, including, vital signs, body weight, laboratory assessments, serious adverse events, adverse events of interest, and adverse events of special interest for the duration of the study. For subjects who prematurely discontinue study drug, sites will be required to make a final contact (eg, schedule the last follow-up visit) at what would have been their final scheduled visit.

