6.1. Adverse Events

Adverse events will be summarized for the 26-week core double-blind treatment period and for the 52-week double-blind treatment phase separately. AEs will be coded using the latest version of the Medical Dictionary for Regulatory Activities (MedDRA) at the time of database lock. Therefore, the preferred terms presented in Attachment 2 may be updated to reflect such updates. A treatment-emergent AE (TEAE) is defined as an adverse event with an onset after the initiation of double-blind study medication and before the last study medication date + 30 days. AEs with a start date prior to initiation of double-blind study medication which are subsequently reported to have either an increase in intensity or change in attribution in relationship to study medication (ie, no attribution to possible, probably, very likely) after the initiation of double-blind study medication will also be considered as TEAEs. Treatment-emergent AEs before the initiation of rescue therapy and TEAEs regardless of rescue therapy will be summarized separately for the 26-week core double-blind treatment period and for the 52-week double-blind treatment phase.

The overall incidence (ie, number and percent of subjects with one or more AE in each category) of AEs, AEs leading to discontinuation of study medication, drug-related AEs, drug-related AEs leading to discontinuation of study medication, serious AEs, serious AEs leading to discontinuation of study medication, serious drug-related AEs, serious drug-related AEs leading to discontinuation of study medication, serious drug-related AEs, serious drug-related AEs leading to discontinuation of study medication, serious drug-related AEs, serious drug-related AEs leading to discontinuation of study medication and deaths, will be summarized by treatment group.

AEs by SOC (ie, number and proportion of subjects with one or more AEs within a SOC) will be summarized by treatment group.

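### The SAP omits the all-adverse-event summary promised in Protocol 11.6, so adverse events more than 30 days after the last dose, and events before the first dose, have no planned by-arm general table

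*Protocol*

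**What the plan says.** Protocol 11.6 (Adverse Events) sets out two outputs. The first is the treatment-emergent analysis: "All reported adverse events with onset during the treatment phase (ie, treatment-emergent adverse events) will be included in the analysis". The second is an addition to it: "a summary of all reported adverse events (regardless of whether treatment-emergent) will also be provided". Details are left to the SAP.

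SAP 6.1 opens by period: "Adverse events will be summarized for the 26-week core double-blind treatment period and for the 52-week double-blind treatment phase separately". It defines a treatment-emergent event as "an adverse event with an onset after the initiation of double-blind study medication and before the last study medication date + 30 days", adding earlier events that later worsen or change attribution. It continues: "Treatment-emergent AEs before the initiation of rescue therapy and TEAEs regardless of rescue therapy will be summarized separately". The overall-incidence, system-organ-class and preferred-term tables that follow refer simply to AEs. No SAP sentence plans a summary of all reported events, and no entry in the SAP amendment history says that it was withdrawn.

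On collection, Protocol 12.2.1 has all adverse events reported from consent to study completion, including in subjects who have stopped drug. Protocol 10.2.4 says that "subjects who discontinue study drug early will be required, wherever possible, to continue with scheduled visits for the duration of the study". For that follow-up it names serious events, events of interest and events of special interest, which is narrower than 12.2.1.

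**The concern.** Overall safety and tolerability is one of the two primary objectives. Stopping drug happens after randomization and may differ by arm, for example if adverse events drive stopping on canagliflozin. Tables that stop counting at a fixed interval after the last dose then observe the arms for unequal time and leave out late events. An all-event table shows whether that matters, and the protocol promised one.

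The omission looks like an oversight. Protocol 11.6 makes a parallel commitment for laboratory and vital-sign data, to be summarized on drug and also regardless of last dose; SAP 6.2 and 6.3 carry both parts over. The primary HbA1c analysis in SAP 5.2.3 also keeps values after treatment discontinuation. The general adverse-event tables have no counterpart.

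**Working it through.** The plan states no figure to reproduce. The check is a comparison of texts, followed by arithmetic on how much follow-up is involved.

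**Which events can reach the SAP's general tables?** There are two readings.

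1. AEs means treatment-emergent events. The tables close 30 days after the last dose.
2. AEs means events in the stated period. SAP 2.1 ends the double-blind treatment phase at the end-of-treatment or early-withdrawal visit, and Protocol 3.1 ends it at the end-of-treatment visit for subjects who stop early. Protocol 10.2.2 asks for that visit at once or as soon as possible after stopping. The tables then usually close even earlier.

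Late off-drug events are left out on both readings. So are events between consent and first dose, unless they later worsen or change attribution.

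**How much off-drug time lies beyond the 30-day window?** Inputs: 52 weeks = 364 days (Protocol 3.1); window 30 days (SAP 6.1). For a stop at week w:

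- off-drug days to Week 52 = 364 − 7w
- days beyond the window = max(364 − 7w − 30, 0)

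| Stop | Off-drug days | Beyond window | Share |
|---|---|---|---|
| Week 6 | 322 | 292 | 91% |
| Week 12 | 280 | 250 | 89% |
| Week 26 | 182 | 152 | 84% |
| Week 34 | 126 | 96 | 76% |
| Week 42 | 70 | 40 | 57% |
| Week 44 | 56 | 26 | 46% |
| Week 48 | 28 | 0 | 0% |

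The share is exactly half when 60 off-drug days remain: day 364 − 60 = 304, about Week 43. For any earlier stop, most off-drug time is outside.

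**Averaged over stop dates (assumed uniform over 364 days).** Mean days beyond the window = 334² / (2 × 364) = 153.2. Mean off-drug days = 364 / 2 = 182. Share = 153.2 / 182 = 84%.

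**Person-years (assumed rates, both arms, everyone followed to Week 52).** Person-years = 146 × rate × 153.2 / 365.25.

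- 5%: 7.3 subjects, 3.1 person-years
- 10%: 14.6 subjects, 6.1 person-years
- 20%: 29.2 subjects, 12.2 person-years

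Full follow-up of 146 subjects is 146 × 364 / 365.25 = 145.5 person-years, so the range is about 2% (3.1 / 145.5) to 8% (12.2 / 145.5) of the total.

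**The case against.** The strongest reply is that a reader might infer that off-drug safety follow-up is never tabulated, and the documents do not support that.

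- Laboratory and vital-sign summaries include all measurements regardless of last dose (SAP 6.2, 6.3), and HbA1c is analysed after discontinuation.
- The listings of deaths and serious events in SAP 6.1 state no last-dose limit. Nor do the summaries of adjudicated fracture, ketoacidosis and pancreatitis, or of amputation from its own form, in SAP 6.1.1.
- The restriction of the main tables to treatment-emergent events is inferred. The preferred-term groupings in 6.1.1, such as malignancy and venous thromboembolism, also state no window.
- SAP silence does not cancel the protocol's promise, so the table might still be produced.

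All of this stands, and it narrows the point to the general adverse-event tables and, depending on how they are read, the 6.1.1 groupings. It does not remove the point. The period reading excludes late events too; listings show cases but give no incidence by arm; and a programmer working from the SAP has no specification for the promised table.

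It is also tempting to take the 10% inflation in Protocol 11.2 as the rate of stopping drug. That figure covers leaving the study. Subjects who leave supply no off-drug follow-up, so it cannot size this gap. Full follow-up to Week 52 is likewise a generous assumption, because Protocol 10.2.4 qualifies it and allows reduced contact.

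**Conclusion.** The point holds as a mismatch between protocol and SAP: a written safety output has no counterpart in the analysis plan. Adverse events beyond the window in subjects who stopped drug, and events before first dose, have no planned general table by arm.

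The size is firm per subject: 84% to 89% of off-drug time for a stop between Weeks 12 and 26, and more than half for any stop before about Week 43. These are shares of time for subjects followed to Week 52, not of events. The total is not known. The 3 to 12 person-years over both arms rest on an assumed 5% to 20% stopping drug, uniform stop dates and complete follow-up; less complete follow-up would lower them.

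Efficacy inference is unaffected. Nor should safety's place among the primary objectives be read as implying a compromised test: SAP 6 plans no hypothesis tests on safety. The omission is worth correcting because it concerns a promised safety display and costs little to restore.

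**What to change.** Add to SAP 6.1 the table that Protocol 11.6 promises: all reported adverse events and serious adverse events from consent to last contact, by system organ class and preferred term, with pre-dose events shown separately. Group subjects by the SAP's safety convention (predominant treatment received, SAP 6), or state why the randomized arm is used. If the sponsor no longer wants the table, amend Protocol 11.6 instead.

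For each general adverse-event table, each preferred-term grouping in 6.1.1, each adjudicated-event summary and each listing, state whether the 30-day window applies. Show days since last dose in the listings. Keep the treatment-emergent tables as the main display.

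Reconcile Protocol 10.2.4 with 12.2.1 on which adverse events are collected after drug is stopped, so that the new table's coverage is clear.

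The cost is a few extra tables from data already collected and a short SAP addition. The downside is that late off-drug events dilute attribution to drug, which is why the new table should be secondary.

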#### **Clinical Laboratory Tests**

Laboratory data will be summarized by type of laboratory test. Reference ranges and markedly abnormal results (to be specified in the SAP) will be referred to in the summary. Descriptive

statistics will be reported for each laboratory analyte at baseline and at each scheduled time point and for change from baseline.

Laboratory analyses will include percent change in lipids (ie, LDL-C, non-HDL-C and total cholesterol) from baseline at Week 26, and percent change in the ratio of LDL-C to HDL-C and non-HDL to LDL-C from baseline at Week 26, and change from baseline in bone turnover markers (serum osteocalcin and serum collagen type 1 CTx) and markers of calcium and phosphate homeostasis (calcium, magnesium, phosphate, PTH, 25-hydroxy Vitamin D, calcitonin; urinary excretion of calcium and phosphate). Additional laboratory parameters (listed in Attachment 7, Clinical Laboratory Tests) will also be analyzed.

## **Hypoglycemic Episodes**

Hypoglycemic episodes are collected on a separate eCRF and are also collected on the adverse event eCRF (for all such events considered as adverse events by the investigator). The primary analysis of hypoglycemia will be based upon data from the hypoglycemia eCRF (and not from the adverse event database). No reconciliation of hypoglycemia data from the adverse event eCRF and the hypoglycemic eCRF will be performed (except to assure that all adverse events of hypoglycemia are also recorded on the hypoglycemia eCRF).

Hypoglycemic episodes will be classified as *either* biochemically documented (ie, a hypoglycemia episode with a concurrent reported glucose value of ≤70 mg/dL [≤3.9 mmol/L]) and/or severe. The primary hypoglycemic analysis of interest will be all biochemically documented hypoglycemic episodes regardless of the presence of symptoms plus all severe hypoglycemic episodes. For each type of hypoglycemia, the percentage of subjects with at least one event will be summarized by treatment group. The hypoglycemic episode rate per subject year exposure, based on the number of episodes adjusted by exposure duration, will be reported by treatment group for each classification of hypoglycemia. (See Attachment 4, Hypoglycemia: Definitions, Symptoms, and Treatment).

#### **Vital Signs**

Descriptive statistics for pulse and sitting blood pressure (systolic and diastolic) values and changes from baseline will be summarized at each scheduled time point. The percentage of subjects with values beyond clinically important limits will be summarized.

#### **Physical Examination**

Physical examination findings will not be summarized except when reported as an adverse event.

#### 12. ADVERSE EVENT REPORTING

Timely, accurate, and complete reporting and analysis of safety information from clinical studies are crucial for the protection of subjects, investigators, and the sponsor, and are mandated by regulatory agencies worldwide. The sponsor has established Standard Operating Procedures in conformity with regulatory requirements worldwide to ensure appropriate reporting of safety information; all clinical studies conducted by the sponsor or its affiliates will be conducted in accordance with those procedures.

For adverse events of interest, investigators will be asked to provide additional information. Adverse events of interest include all malignancies, severe hypersensitivity reactions (eg, angioedema, anaphylaxis, Stevens-Johnson syndrome), photosensitivity reactions, serious adverse events of hepatic injury, nephrotoxicity/acute kidney injury, venous thromboembolic events, fractures, and pregnancy.

The following adverse events have been designated as adverse events of special interest and need to be reported to Janssen within 24 hours of becoming aware of the event, which is the same timeframe for reporting of serious adverse events. These adverse events must be reported using a supplemental reporting form, to complement standard information collected on the Adverse Event/SAE eCRF, together with the SAE report for serious events.

- Diabetic ketoacidosis and adverse events related to DKA, ketoacidosis, metabolic acidosis or acidosis
- Amputations
- Pancreatitis
- Serious adverse events of UTIs including urosepsis and pyelonephritis

Additional information and documentation will be requested from investigators to support a detailed assessment of all deaths. Investigators may also be asked to provide additional information on other adverse events, based upon review by the MSRC. If adverse events of interest are identified in the future, guidance concerning the reporting of those events may be provided to investigators via appropriately-documented study communications.

#### 12.1. Definitions

#### 12.1.1. Adverse Event Definitions and Classifications

#### **Adverse Event**

An adverse event is any untoward medical occurrence in a clinical study subject administered a medicinal (investigational or non-investigational) product. An adverse event does not necessarily have a causal relationship with the treatment. An adverse event can therefore be any unfavorable and unintended sign (including an abnormal finding), symptom, or disease temporally associated with the use of a medicinal (investigational or non-investigational) product, whether or not related to that medicinal (investigational or non-investigational) product. (Definition per International Conference on Harmonisation [ICH].)

This includes any occurrence that is new in onset or aggravated in severity or frequency from the baseline condition, or abnormal results of diagnostic procedures, including laboratory test abnormalities.

**Note**: The sponsor collects adverse events starting with the signing of the ICF (refer to Section 12.2.1, All Adverse Events, for time of last adverse event recording).

#### **Serious Adverse Event**

A serious adverse event based on ICH and EU Guidelines on Pharmacovigilance for Medicinal Products for Human Use is any untoward medical occurrence that at any dose:

- Results in death
- Is life-threatening
  (The subject was at risk of death at the time of the event. It does not refer to an event that hypothetically might have caused death if it were more severe)
- Requires inpatient hospitalization or prolongation of existing hospitalization
- Results in persistent or significant disability/incapacity
- Is a congenital anomaly/birth defect
- Is a suspected transmission of any infectious agent via a medicinal product
- Is Medically Important\*

\*Medical and scientific judgment should be exercised in deciding whether expedited reporting is also appropriate in other situations, such as important medical events that may not be immediately life-threatening or result in death or hospitalization but may jeopardize the subject or may require intervention to prevent one of the other outcomes listed in the definition above. These should usually be considered serious.

A serious and unexpected adverse event occurs for which there is evidence suggesting a causal relationship between the study drug and the event (eg, death from anaphylaxis), the event must be reported as a serious and unexpected suspected adverse reaction even if it is a component of the study endpoint (eg, all-cause mortality).

#### **Unlisted (Unexpected) Adverse Event/Reference Safety Information**

An adverse event is considered unlisted if the nature or severity is not consistent with the applicable product reference safety information. For canagliflozin, the expectedness of an adverse event will be determined by whether or not it is listed in the IB.

#### 12.1.2. Attribution Definitions

#### **Not Related**

An adverse event that is not related to the use of the study drug.

#### Doubtful

An adverse event for which an alternative explanation is more likely, eg, concomitant drug(s), concomitant disease(s), or the relationship in time suggests that a causal relationship is unlikely.

#### **Possible**

An adverse event that might be due to the use of the study drug. An alternative explanation, eg, concomitant drug(s) or disease(s), is inconclusive. The relationship in time is reasonable; thus, the causal relationship cannot be excluded.

#### **Probable**

An adverse event that might be due to the use of the study drug. The relationship in time is suggestive (eg, confirmed by dechallenge). An alternative explanation is less likely, eg, concomitant drug(s), concomitant disease(s).

# Very Likely

An adverse event that is listed as a possible adverse reaction and cannot be reasonably explained by an alternative explanation, eg, concomitant drug(s), concomitant disease(s). The relationship in time is very suggestive (eg, it is confirmed by dechallenge and rechallenge).

#### 12.1.3. **Severity Criteria**

An assessment of severity grade will be made using the following general categorical descriptors:

Mild: Awareness of symptoms that are easily tolerated, causing minimal discomfort and not interfering with everyday activities.

**Moderate**: Sufficient discomfort is present to cause interference with normal activity.

Severe: Extreme distress, causing significant impairment of functioning or incapacitation. Prevents normal everyday activities.

The investigator should use clinical judgment in assessing the severity of events not directly experienced by the subject (eg, laboratory abnormalities).

#### 12.2. **Procedures**

#### 12.2.1. **All Adverse Events**

All adverse events and special reporting situations, whether serious or non-serious, will be reported from the time a signed and dated ICF is obtained until completion of the study (including subjects who discontinue study drug treatment).

Data will be collected in source documents and on the eCRF for all adverse events.

All deaths will also be recorded.

For adverse events of interest (see Section 9.8, Safety Evaluations) a supplemental eCRF will be used to collect additional information. Investigators may be asked to provide additional information on adverse events, based upon review by the MSRC or the IDMC.

CONFIDENTIAL – FOIA Exemptions Apply in U.S.

Serious adverse events, including those spontaneously reported to the investigator within 30 days after the last dose of study drug, must be reported using the Serious Adverse Event Form, which must be completed and signed by a member of the study-site personnel, and transmitted to the sponsor within 24 hours. The sponsor will evaluate any safety information that is spontaneously reported by an investigator beyond the time frame specified in the protocol.

All events that meet the definition of a serious adverse event will be reported as serious adverse events, regardless of whether they are protocol-specific assessments.

All adverse events, regardless of seriousness, severity, or presumed relationship to study drug, must be recorded using medical terminology in the source document and the eCRF. Whenever possible, diagnoses should be given when signs and symptoms are due to a common etiology (eg, cough, runny nose, sneezing, sore throat, and head congestion should be reported as "upper respiratory infection"). Investigators must record in the eCRF their opinion concerning the relationship of the adverse event to study therapy. All measures required for adverse event management must be recorded in the source document and reported according to sponsor instructions.

Study research staff should make study subjects aware of potential signs and symptoms of DKA such as difficulty breathing, nausea, vomiting, abdominal pain, feeling confused, fruity-smelling breath, and unusual fatigue or sleepiness. Study subjects should be instructed to contact the site if they experience such symptoms. If the investigator suspects these symptoms may be related to DKA (even if the subject's blood glucose levels are <250 mg/dL (<13.9 mmol/L), testing for urine or blood ketones should be considered.

Consistent with standard diabetes treatment guidelines, all study subjects should be provided with routine preventative foot care and early intervention for foot problems. Specifically:

- Provide or ensure that all subjects have had general foot self-care education.
- Perform a comprehensive foot evaluation (at Day 1, Week 26, and Week 52 visits) to identify risk factors for ulcers and amputations. The examination should include inspection of the skin, assessment of foot deformities, neurological assessment including pinprick or vibration testing or assessment of ankle reflexes, and vascular assessment including pulses in the legs and feet.
- Subjects who have a history of prior lower-extremity complications, loss of protective sensation, structural abnormalities, or peripheral arterial disease should be referred to foot care specialists for ongoing preventative care.

For all study subjects, there should be a clinical evaluation at every visit to assess the presence of any sign or symptom suggestive of volume depletion (eg, hypotension, postural dizziness, orthostatic hypotension, syncope, and dehydration), which if present should be adequately treated either by decreasing dose or eliminating use of diuretics or other antihypertensive medications or interrupting study drug until the condition resolves.

The sponsor assumes responsibility for appropriate reporting of adverse events to the regulatory authorities. The sponsor will also report to the investigator (and the head of the investigational institute where required) all suspected unexpected serious adverse reactions (SUSARs). The investigator (or sponsor where required) must report SUSARs to the appropriate IEC/IRB that approved the protocol unless otherwise required and documented by the IEC/IRB. A SUSAR will be reported to regulatory authorities unblinded. Participating investigators and IEC/IRB will receive a blinded SUSAR summary, unless otherwise specified.

Subjects (or their designees, if appropriate) will be provided with a "study card" indicating the name of the investigational study drug, the study number, the investigator's name, a 24-hour emergency contact number, and, if applicable, excluded concomitant medications.

For all studies with an outpatient phase, including open-label studies, the subject must be provided with a "wallet (study) card" and instructed to carry this card with them for the duration of the study indicating the following:

- Study number
- Statement, in the local language(s), that the subject is participating in a clinical study
- Investigator's name and 24-hour contact telephone number
- Local Sponsor's name and 24-hour contact telephone number (for medical staff only)
- Site number
- Subject number
- Any other information that is required to do an emergency breaking of the blind

